Subject Population	Pediatric and adult patients up to 35 years old, of any gender, and ethnic background, with malignant and/or non-malignant diagnosis that are treatable though allogeneic stem cell transplantation.

Inclusion Criteria:

- Participants greater than one month of age.
- Participant has a disorder that can be treated with a hematopoietic stem cell transplant
 - Participant's is eligible for an allogenic HSCT as per current institutional SOP and FACT standards
- Participant must have a related or unrelated matched or mismatchedrelated donor who is:
 - Able to receive granulocyte colony-stimulating factor (G-CSF) and undergo apheresis either through placement of catheters in antecubital veins or a temporary central venous catheter OR agrees on a bone marrow harvest;
 - Healthy as per donor selection screening (following current SOP based on standards of foundation for accreditation of cellular therapy and stem cell transplantation – FACT);
 - Willing to participate and sign consent.
- Participant or Legal Authorized Representative is able to sign informed consent (and signed assent, if applicable) for transplant.

Exclusion Criteria:

- Participant does not qualify for an allogeneic transplant due to medical screening, underlying disease, or lack of alternative donors.
- Any condition that compromises compliance with the procedures of this protocol, as judged by the principal investigator.

Principal Investigator will evaluate and report all grade 3 or 4 adverse reactions that are unexpected and possibly related to the investigation in process and are not expected TRM as per protocol definition. If it becomes clear that the study treatment is less effective than other available treatments or the toxicity is unacceptable we will follow the stopping rules.

Stopping rule for primary graft failure: The first 30 enrolled patients (related and unrelated) will be evaluated for the stopping rule for primary graft failure. The trial is stopped if there are ≥ b graft failures out of k resolved patients. Only points where stopping is possible are listed.

Discontinuation Criteria (Safety Considerations)

Eligibility criteria

k	2	4	5	6	8	9	10	12	13	14	15	16	18	19	20	21	23	24	25	26	27	28	30
b	2	3	3	3	4	4	4	5	5	5	5	5	6	6	6	6	7	7	7	7	7	7	8

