Serious Adverse Event (SAE): Any adverse event occurring that results in any of the following outcomes: death, a life threatening adverse event, a persistent or significant disability/incapacity, a congenital anomaly, requires intervention to prevent permanent impairment or damage. Unless the Principal Investigator is using an investigational agent, s/he is not bound by the definition in Title 22 CFR. Stanford IRB definition(s) and requirements apply when applicable, Unanticipated Problems Involving Risks to Participants or Others (UPs) and Unanticipated Adverse Device Effect (UAD)

All grades 3-5 organ-related adverse events not due to the primary malignancy or pre-existing condition will be collected from day 0 through resolution of the SAE. Grade 4 infusion reactions will be reported expeditiously and as a separate listing in the FDA Annual Report.

Distinction between Serious and Severe Adverse Events: The term severe is used to describe the intensity (severity) of a specific event, for example mild, moderate or severe. The event itself however, may be of relatively minor medical significance, for example a severe headache. This is not the same as serious, which is based on the patient/event outcome and is usually associated with events that pose a threat to the patient's life or functioning. Seriousness, not severity, serves as a guide for defining regulatory obligations.

All Adverse events will be graded using the NCI Common Terminology Criteria for Adverse Events (CTCAE) version 4.3 found on the following website:

http://ctep.cancer.gov/reporting/ctc.html

The Principal Investigator (PI) or designee will assess each Adverse Event (AE) to determine whether it is expected or unexpected according to the Informed Consent, Protocol Document, or Investigator's Brochure; and its

relationship to the investigational product.

For the purpose of this study, only AE's found to be directly related to a study-mandated intervention will be captured. The following adverse events, if felt to be related to study treatment, will be captured, but not reported as SAEs:

- Hospitalization, prolongation of hospitalization, or escalation of care due to study-mandated intervention
- Disease Relapse
- Any problems with CliniMACS device during cell separation or inability to achieve CD34+ cell and CD3+ cell target doses
- Any positive culture of HSCT product
- Failure to engraft or graft rejection

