All Serious Adverse Events (SAEs) will be tracked until resolution. SAEs will be collected from the time of stem cell infusion until 30 days post cell infusion. SAEs will be reported to the IRB if they meet the definition of expedited reporting per institutional regulations. All AE's and SAE will be reported at continuing renewal.

Reports (copy of faxed MedWatch) will also be sent to Miltenyi Biotec Incorporated, to the director of Regulatory Affairs and Safety Officer at [contact].

Serious Adverse events will be reported on the MedWatch form 3500a when it meets the definition of expedited FDA reporting. All deaths will be examined to determine if they are related to the use of the CliniMACS device or infusion of manipulated product. If the death is determined to be related, the event leading to the death must be reported within 24 hours of the Investigator's awareness of the event.

The following SAEs require expedited reporting (as soon as possible but within at least 7 calendar days of the investigator learning of the event):

Deaths: All deaths up to 100 days post-transplant. This includes deaths from the common and expected grade 3-4 toxicities noted below. Deaths that occur outside of Stanford will be reported within 5 working days of knowledge of the death. It must be noted that obtaining detailed information on the cause and circumstances of a death occurring at another institution can be difficult. Excludes deaths related to relapse of underlying disease, which will reported in the annual report.

All serious and unexpected toxicities defined as those toxicities not identified in the transplant literature or in the consent form and that are felt to be related to protocol-mandated procedures.

The following will not be reported as SAEs:

- Hospitalizations: Approximately 50% of allogeneic transplant recipients will be readmitted to the hospital. The
 most common indications for readmission of an allogeneic HCT recipient are fever, failure to maintain nutritional
 status and graft versus host disease. Only hospitalizations felt to be related to study mandated interventions
 should be reported as SAE's.

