- Relapse of disease: Disease relapse unfortunately remains a significant problem following both autologous and allogeneic transplantation. The risk of relapse is influenced by both patient and disease variables. The risk of relapse following allogeneic transplant is extremely dependent on the disease being treated but ranges from 10% (for patients with severe aplastic anemia) to 80% (for patients with refractory acute leukemia).
- Common and expected grade 3 4 toxicities of HSCT that are well described in the transplant literature, the product inserts or stated in the consent form and do not result in death. This includes but is not limited to neutropenia, thrombocytopenia, anemia, thrombotic microangiopathy, bleeding requiring transfusions, edema, hypertension, hypotension, gastritis, mucositis, nausea, vomiting, diarrhea, hematuria, central venous catheter infections, febrile episodes, sepsis, mental status changes, insomnia, mood alterations, seizures, tremor, pain, hypoxia, pleural effusion, pneumonitis, incontinence, infertility, laboratory abnormalities, veno-occlusive disease, graft failure, cardiac arrhythmias and graft versus host disease.
- Secondary Malignancies. The occurrence of secondary malignancies and associated mortality is a known risk of cancer therapies. The occurrence of secondary malignancies will be reported in the annual report.

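### Section 8.2 contradicts itself on which adverse events are captured and on whether related hospitalisations are SAEs, and its related-only sentence does not fit the week-4 halt rule

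*Combined protocol and SAP*

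**What the plan says.** **Capture of adverse events.** Section 8.2 states: "All grades 3-5 organ-related adverse events not due to the primary malignancy or pre-existing condition will be collected from day 0 through resolution" (the sentence ends by referring to resolution of the SAE). A few paragraphs later it states: "For the purpose of this study, only AE's found to be directly related to a study-mandated intervention will be captured". The section's own definition of an adverse event requires no causal relationship. The Synopsis, under its safety considerations, sets attribution differently again: "Principal Investigator will evaluate and report all grade 3 or 4 adverse reactions that are unexpected and possibly related to the investigation in process".

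**Related hospitalisation.** Section 8.2 introduces a list with "The following adverse events, if felt to be related to study treatment, will be captured, but not reported as SAEs". Its first item is "Hospitalization, prolongation of hospitalization, or escalation of care due to study-mandated intervention". Further on, under events that are not to be reported as SAEs, an exception begins "Only hospitalizations felt to be related to study mandated interventions", and the sentence goes on to say that these should be reported as SAEs.

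**Halt rule.** The Synopsis and Section 10.2 halt the protocol if any patient has grade IV or higher acute GvHD, grade IV or higher infection, or any unexpected grade IV or higher toxicity by 4 weeks after transplant. The rule sets no relatedness condition and names no form or listing as its input.

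**The concern.** Two members of staff who both follow Section 8.2 could treat the same event differently. One would record a grade 4 organ toxicity attributed to conditioning and the other would leave it out. One would report a related admission as an SAE and the other would not. Section 8.2 expects about half of allogeneic recipients to be readmitted, so the admission question will come up, although the documents do not say what share of readmissions would be judged related.

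The capture conflict also matters for patient safety. The halt rule acts on a single patient and ignores attribution. A filter on attribution ahead of it could remove from the adverse event record an event that the rule is required to count.

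**Working it through.** No arithmetic settles this. The check sets the instructions side by side for two test events.

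**Event 1: an unexpected grade 4 organ toxicity within 4 weeks, attributed to conditioning.** Section 4.1 leaves conditioning to disease and institutional guidelines, so such an event can reasonably be judged not directly related to a study-mandated intervention.

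| Instruction | Attribution test | Result for event 1 |
|---|---|---|
| Section 8.2, grade 3 to 5 sentence | Not due to malignancy or pre-existing condition | In |
| Section 8.2, related-only sentence | Directly related to a study-mandated intervention | Out |
| Synopsis, investigator reporting | Unexpected and possibly related | In or out, depending on a lower threshold |
| Synopsis and Section 10.2, halt rule | None | Counts, and halts the protocol |

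The first two rows give opposite answers. The documents draw no distinction between collecting and capturing an event, and no sentence says which rule prevails.

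Can the grade 3 to 5 sentence be confined to SAEs, since it ends by mentioning the SAE? That does not clearly remove the conflict. Section 8.2 defines an SAE as "Any adverse event occurring that results in any of the following outcomes", so SAEs are a subset of adverse events and a limit on adverse events reaches them on its face.

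Does the SAE route cover the halt window? SAEs are collected from infusion to day 30, and 4 × 7 = 28 days, so the window is long enough. But Section 8.2 separates severity from seriousness. A grade IV event is therefore not automatically an SAE, and the SAE route is not a full substitute for adverse event capture.

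**Event 2: a hospitalisation due to a study-mandated intervention.**

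| Instruction in Section 8.2 | Result for event 2 |
|---|---|
| List of related events captured only | Not reported as an SAE |
| Exception under hospitalisations | Reported as an SAE |

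These are opposite instructions for the same event. The SAE definition does not resolve them, because hospitalisation is not among its listed outcomes.

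**The case against.** The strongest reply is that the halt rule has other sources of information. Infections are a secondary endpoint described by incidence and type, with no relatedness test. Section 9 sends toxicity data to CIBMTR and REDCap and has the investigator review data for safety. Section 11.2 provides study case report forms. SAEs are collected to day 30, and most deaths to day 100 need expedited reporting whatever their cause. Section 8.2 also has the investigator or designee assess each adverse event for expectedness and relationship, which is the judgement that the unexpected-toxicity trigger needs. A workable reading is that the SAE sentences govern SAEs and the related-only sentence governs the rest.

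Much of this stands. A reader might infer that a non-fatal grade IV sepsis would leave no record, because Section 8.2 names "central venous catheter infections, febrile episodes, sepsis" among common and expected events not reported as SAEs. The documents do not support that inference: the list limits reporting, not collection, and infections are recorded as an outcome. The same list covers only expected events, so it cannot remove an unexpected toxicity.

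The reply does not remove the contradictions. The workable reading has to be supplied by the reader, because Section 8.2 does not state it. Even on that reading, a grade IV toxicity that is neither serious nor directly related stays outside adverse event capture, and no section ties CIBMTR, REDCap or the investigator's review to the halt rule. Nothing in the reply touches the hospitalisation conflict.

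**Conclusion.** Wrong as written: an internal inconsistency in two places in Section 8.2, with a consequence for the halt rule. Both contradictions rest on the text alone. The halt-rule consequence is conditional: it follows if the related-only sentence governs capture, and it falls mainly on unexpected grade IV or higher toxicity not judged directly related.

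No numerical size can be given. The documents state neither a rate of such events nor the share that would be judged related. What can be said is that the threshold is one patient in a planned 30, so the rule leaves no margin for an event handled inconsistently.

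A reader might go further and infer that halts will be missed or that endpoints are under-counted. The documents do not support either. Acute GvHD, which is the primary endpoint and also a halt trigger, is graded under Appendix A, and the secondary outcomes have their own data routes.

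**What to change.** 1. Reconcile the two capture sentences in Section 8.2. Make relatedness a recorded field rather than a filter on capture of grade IV or higher events up to week 4, and use one defined attribution term in Section 8.2 and the Synopsis.
2. State that grade IV or higher infections and toxicities up to 4 weeks after transplant are recorded regardless of attribution, and that this record feeds the halt rule in Section 10.2. Name infections explicitly, because the grade 3 to 5 sentence is limited to organ-related events.
3. Reconcile the two statements on related hospitalisation so that only one applies.

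The cost is protocol wording and modest extra case report form entry in the first 4 weeks. Sample size, visits, the halt rule itself and the primary endpoint are unchanged.

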In a retrospective review of the experience of 3 investigators in the U.S. (Cowan, Gilman, Sleight) with alternative (haplocompatible) donor transplant using CD34+ cell selection for T cell depletion, 13/18 (72%) were surviving with follow-up of 7 months – 7 years (median 31 months)(22). The median patient age was 8 years (range 1-20). Patient with malignancy (n=13) included: AML - CR1 (primaryinduction failure, failed cord blood transplant) [1], CR2 [3]; MDS - RA/RARS [2], RAEB [2]AM (and Fanconi anemia, FA) [1]; CML - CP2 [1]; ALL - CR3 [2]; NHL - CR2 [1]. Patients with non-malignant (n=5) disease included severe aplastic anemia (1 with prior bone marrow transplant three years earlier) [4] and Wiskott-Aldrich syndrome [1].

Fourteen donors were a 3/6 HLA match and 5 were a 4/6 match (one patient had two transplants using different donors). A CD34-positive selection device – Miltenyi CliniMACS $^{\otimes}$ (15), Isolex (3) – was used to select stem cells and deplete T lymphocytes. Patients received a median of 18 x 10 6 CD34+ (stem) cells/kg (range 6-28) and 3 x 10 4 CD3+ (T) cells/kg (range 0.3-11).

Sustained primary engraftment occurred in 15/18 (83%) patients. Primary graft failure occurred in one patient. Two patients had immunological rejection following HHV-6 reactivation. They both engrafted after a second transplant; therefore the overall engraftment rate was 94%. The median time to an ANC >0.5 x 10⁹/L was 12 days (range 9-21). Platelet recovery occurred in 16/18 at a median of 17 days (range 9-22). Grade II acute GvHD was seen in 4/17 patients (24%). Grade III-IV acute GvHD was seen in 1 pt. (6%) with overlap syndrome (acute + chronic GvHD) associated with HHV-6 reactivation. Nine patients received DLI and/or stem cell boosts (boosts for graft rejection); 4 had grade II GvHD (3/4 had a history of acute GvHD) and none had grade III-IV GvHD. After DLI and/or stem cell boost, two patients developed extensive chronic GvHD and one developed overlap syndrome. The day 100 mortality and one year transplant-related mortality were 11% and 19%, respectively. Four patients (of 13 at risk, 31%) have relapsed; 1 patient with cytogenetic relapse is in CR > 1 year later. The 2 year predicted survival is 64% (60% for 13 patients with malignant disease and 75% for 5 patients with non- malignant disease).

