Infections were common. All patients were at risk for CMV reactivation. Seven patients (39%) reactivated CMV. All cases were responsive to anti-viral therapy and/or DLI. No CMV disease was seen. Seven patients had adenovirus reactivation and six had HHV-6 reactivation. EBV reactivation occurred in 5/18 (28%) patients, three of whom manifested signs of post-transplant lymphoproliferative disorder.

Patients received a median of 3×10^4 CD3+ cells/kg at the time of transplant. Some patients received additional donor T cells (DLI) for viral reactivation. At three months post-transplant, only 4 of the 15 evaluable patients had a CD4 count > 100. By nine months post-transplant, 10 of the 13 evaluable patients had a CD4 count > 200.

There is an ongoing study at the University of California, San Francisco Medical Center of a prospective trial of CD34+ selected (with the CliniMACS® device) PBSC from mismatched related donors (protocol CC# 01151). Patients received a conditioning regimen including TBI 1200 cGy, thiotepa, fludarabine, and rabbit-ATG (3.5 mg/kg). Patients received a fixed T cell dose of 3 x 10⁴/kg at the time of transplant. Seventeen evaluable patients have been reported with the following diagnoses: ALL (3), AML (6), biphenotypic leukemia (1), CML (1), MDS (1), aplastic anemia (2), congenital amegakaryocytic thrombocytopenia (1) combined immunodeficiency (1), and hemophagocytic lymphohistiocytosis (1).

Twelve of the 17 (65%) were alive and well as of 2010, with follow-up ranging from 3 months to 6.5 years (median follow-up 2.5 years). Survivors include 7/12 (58%) with malignant disease and 5/5 (100%) with non-malignant disease. One patient died at 7 months after transplant due to parainfluenza and Paecilomyces infections and

[figure not shown]
another died at 23 months after transplant due to disseminated Mucor infection, a fungus from the class of Zygomycetes. There was no severe (grade III/IV) acute GvHD. Only 3/17 (18%) of patients achieved > 100 CD4+ T cells/uL by 100 days after transplant and 3/4 of these patients either had received donor T cell infusion for serious viral infections prior to 100 days or had GvHD (in which case the T cells probably represented those causing the GvHD and not providing protection against infection).

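### Section 8.2 sets conflicting safety windows, so it is unclear whether non-fatal serious events starting on days 31 to 100 are collected as SAEs

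*Combined protocol and SAP*

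**What the plan says.** Section 8.2 (Adverse Event Reporting) contains four rules that bear on when a serious event counts.

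- **SAE window.** "SAEs will be collected from the time of stem cell infusion until 30 days post cell infusion". SAEs already collected are then tracked until they resolve.
- **Deaths.** Among the SAEs that need expedited reporting: "Deaths: All deaths up to 100 days post-transplant". There is an exception: "Excludes deaths related to relapse of underlying disease, which will reported in the annual report".
- **Unexpected toxicities.** Serious toxicities that are not described in the transplant literature or consent form, and are thought related to protocol procedures, also need expedited reporting. No time limit is given.
- **Grade 3-5 organ-related events.** Those not due to the malignancy or a pre-existing condition "will be collected from day 0 through resolution of the SAE".

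The section's SAE definition includes death: "Any adverse event occurring that results in any of the following outcomes: death, a life threatening adverse event".

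Two further provisions in 8.2 act as filters. Adverse event capture is restricted to events directly related to a study-mandated intervention. Common, expected, non-fatal grade 3-4 transplant toxicities are not reported as SAEs.

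Elsewhere, the synopsis sets the primary endpoint (grade III/IV acute GvHD) at Day +100 and TRM at Day 100 and one year. It lists severe toxicities as a secondary endpoint with no time window. Section 4.4 ends participation at day 100, while the synopsis speaks of at least one year.

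**The concern.** Staff cannot apply all of these rules as written. If SAE collection stops at day 30, a death on day 60 that must be reported as an SAE has no place in SAE collection. For non-fatal events the position is less clear still, because the rules that reach past day 30 either cover only part of them or can be read in two ways.

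Two things are at stake. The incidence of severe toxicities has no window of its own, so its value may depend on which 8.2 rule the data staff follow. Section 4.3 also lets the investigator end the study for significant toxicities related to the graft, without a time limit, and that judgement needs data from after day 30.

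The protocol's own background shows that immune deficiency after such grafts lasts beyond the first month. In the retrospective review, "At three months post-transplant, only 4 of the 15 evaluable patients had a CD4 count > 100". Section 2.1 also concludes that immune recovery was slow and that infections contributed to morbidity and mortality. These are reasons to want a clear record after day 30. They do not measure how many serious events start in that period.

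**Working it through.** The plan gives no figure to reproduce. The check sets the rules side by side and applies them to test cases.

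**Length of the unclear period.** The SAE window ends at day 30. The death rule, the primary endpoint and the first TRM time point end at day 100. Days outside the SAE window: 100 − 30 = 70. Share of the primary endpoint period: 70 / 100 = 70%.

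**Case 1: non-relapse death on day 60.**
- SAE by definition: yes.
- Expedited report required: yes, because 60 ≤ 100.
- Inside the SAE collection window: no, because 60 > 30.

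The section contradicts itself here.

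**Case 2: relapse death on day 60.** It is excluded from the expedited rule and goes to the annual report, so the contradiction in Case 1 concerns non-relapse deaths only.

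**Case 3: serious, related, unexpected, non-fatal toxicity starting on day 60.**
- Expedited report required: yes, with no time limit.
- Inside the SAE collection window: no.

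The event is reportable, but the two rules again disagree.

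**Case 4: non-fatal life-threatening infection starting on day 60, of a kind known in the transplant literature.**
- SAE window: outside.
- Death rule: does not apply.
- Unexpected-toxicity rule: does not apply, because the event is known.
- Grade 3-5 rule: unclear. The wording may fix when an event must start, or only how long it is followed. It covers organ-related events, and the relatedness restriction follows it.
- Endpoint data: the infection is recorded by incidence and type.

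The infection is therefore study data, but the text does not settle whether it is collected as an SAE.

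**Stopping rules.** The grade IV halting rule in section 10.2 runs to 4 weeks, 4 × 7 = 28 days. As 28 < 30, it lies inside the SAE window and is unaffected.

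**The case against.** The strongest reply is that little is lost. Non-relapse deaths to day 100 and serious unexpected related toxicities are reportable after day 30 whatever the collection sentence says. Infections, PTLD, severe toxicities and TRM are secondary endpoints, section 2.4 adopts the standard CIBMTR follow-up schedule and forms, and section 9 has toxicity entered into CIBMTR and REDCap. The relatedness restriction and the list of expected toxicities, which names sepsis, pneumonitis and GvHD among others, would keep many infections out of SAE reports on day 10 as well as on day 60.

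Most of this stands, and it rules out two stronger readings. A reader might infer that all serious events on days 31 to 100 go uncollected, or that the safety summary would be flattering. The documents support neither, because several rules and endpoints reach past day 30.

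A reader might also try to size the gap from the review cited in section 2.1: "The day 100 mortality and one year transplant-related mortality were 11% and 19%, respectively". That gives 30 × 0.11 = 3.3 expected deaths by day 100. But the figure rests on 18 patients, about 2 deaths (0.11 × 18 = 1.98), and the documents do not say how many fell after day 30. Non-relapse deaths are also the category already reportable to day 100. The infection deaths at 7 and 23 months in section 2.1 lie beyond Day +100, and the PTLD cases there are undated, so neither shows risk within days 31 to 100.

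The reply does not remove the contradiction over deaths or the ambiguity over non-fatal events. Recording an infection as an endpoint is not the same as recording its seriousness, relatedness and outcome as an SAE.

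**Conclusion.** The point holds as an internal conflict in section 8.2. A non-relapse death on days 31 to 100 is a reportable SAE outside the SAE collection window. Whether non-fatal serious events starting on those 70 days are collected as SAEs cannot be determined from the text. The contradiction over deaths is plain from the wording and needs no assumption. The extent of the gap for non-fatal events depends on how the grade 3-5 sentence is read and on the two filters, and the documents give no basis for counting affected events. The consequence is a safety record that could be incomplete, and a severe toxicities endpoint whose period is undefined. The conflict should be corrected before the safety data are summarised.

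**What to change.** In section 8.2:

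- Move the end of the SAE collection window from day 30 to Day +100, which matches the death rule, the primary endpoint and the first TRM time point.
- Keep the rule for serious unexpected related toxicities without a time limit.
- Reword the grade 3-5 sentence to say that events with onset at least through Day +100 are collected and then followed to resolution. The words 'at least' matter: the present sentence states no end of onset, and a flat Day +100 limit could shorten collection that was meant to run longer.

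In the synopsis, give the severe toxicities endpoint the same window.

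The cost is short text changes and SAE entry by the same staff for about 70 more days per patient. With 30 recipients that is at most 30 × 70 = 2,100 patient-days, within follow-up already planned to Day +100. The change leaves the relatedness restriction and the expected-toxicity list as they are, so it settles the window but does not make every late infection an SAE.
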